8.4.2 Early Termination/Discontinuation

The following data from subjects discontinuing before randomization (i.e. screen failures) will be captured in the eCRF:

- Demographics
- AEs / SAEs
- Reason for discontinuation (including applicable assessment results)

If a randomized subject is discontinued from the trial prior to Visit 4 (Day 57 ± 2) and not willing to perform all subsequent visits and assessments, then all evaluations planned for

Visit 4 should be performed on the day of discontinuation (early termination) or at the discretion of the investigator.

Randomized and dosed subjects who discontinue treatment for any reason will be encouraged to undergo all subsequent trial visits and assessments.

Data from subjects discontinuing after randomization will be captured completely in the eCRF including Early Termination Visit and reason for discontinuation.

8.4.3 Unscheduled Visits

An unscheduled visit may be performed during the course of the trial in order to ensure subject safety and/or to dispense additional IMP if necessary (i.e. damaged/lost or subject ran out of IMP in between visits). All procedures performed at an unscheduled visit will be recorded in the source documents and on the unscheduled visit eCRF pages. Any unscheduled visit procedure listed in the eCRF that is not performed should be indicated as “not done.”

Evaluations that may be conducted at an unscheduled visit include:

- Slit-Lamp biomicroscopy;
- Visual acuity;
- Intraocular pressure;
- Dilated fundoscopy;
- Urine pregnancy test (for women of childbearing potential);
- Assessment of AEs;
- Assessment of concomitant medications and/or treatments; and
- Any other assessments needed in the judgment of the investigator.

8.5 Compliance with Protocol

Subjects will be instructed on proper instillation and storage of IMP at Visits 1, 2, and 3, and provided with written instructions ([Appendix 2](#)). The used and unused IMP bottles will be collected from subjects at visits 2, 3 and 4 to assess subject dosing compliance.

Subject dosing compliance will be determined by the subject’s response or lack thereof to the prompt “Was the dose taken?” in the subject diary. If more than 20% of the responses to the total expected dose-taken prompts are checked “no,” left blank, or missing, then the subject will be deemed noncompliant for dosing and a deviation recorded e.g., 12 checked “no,” left blank, or missing at Visit 2 and Visit 3 and more than 24 at Visit 4.

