4.3 Visit Description

Subjects will be required to sign an Informed Consent before completing any trial related procedures. All trial procedures are listed in [Section 8.4](#) and in the schedule of assessments [Appendix 1](#). The ocular symptoms assessments and evaluations must be performed in the respective order as listed. IMP Dispensation is described in [Section 7.1.4](#).

Subjects will be instructed not to show or discuss the properties of the assigned IMP and/or their experience with the IMP with other trial participants, and not to show or discuss the IMP with the Investigator or site staff other than the dedicated dosing coordinator, unless instructed to do so.

Screening (Visit 0)

All assessments required for the screening visit must be done within 14 days before the randomization, baseline Visit 1. At least one eye must qualify with all of the following objective measures: Tear film break up time ≤ 5 sec, Schirmer's Test ≥ 5 mm, Meibomian gland dysfunction (MGD) defined as MGD score ≥ 3 , and total Corneal Fluorescein Staining (CFS) of $4 \leq x \leq 11$. Subjects who fail to qualify for the trial at screening may be rescreened as described in [Section 5.5](#).

Baseline Day 1 (Visit 1)

On Day 1 (Visit 1), eligible subjects will be evaluated for baseline signs and symptoms of dry eye disease and will be randomized to NOV03 QID or saline solution QID. Subjects will be given a 14-day supply and will self-administer a single drop of the first initial trial medication into each eye at the clinic. Subsequently the subject will be asked to complete an instillation comfort questionnaire. Each subject will be given a dosing diary to record

dosing. Study staff will help the subject to understand how to use the dosing diary and when the remaining doses should be taken.

Visits 2-4 / (ET)

Subjects will return to the clinic on Day 15±1 (Visit 2), 29±2 (Visit 3), and 57±2 (Visit 4/Early Termination (ET)) to be evaluated for signs and symptoms of dry eye disease. The subject will be asked to complete an eyedrop acceptability questionnaire during Visit 4. Collection and review of IMP will be performed (used and unused trial medication should be returned to the clinic) and new trial medication will be dispensed at Visit 2 and Visit 3. The dosing diary will be collected at the clinic during each visit and checked for compliance. Subjects will be discharged from the trial after all Visit 4/ET assessments have been completed.

Early Termination

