7.1.5 Instructions for Use and Administration

At Visit 1 subjects will be instructed by the dedicated dosing coordinator on appropriate hygiene and eye drop dosing technique. Subjects will self-administer NOV03 or saline eye

drops in each lower cul-de-sac of each eye as shown in Appendix 2 under the supervision of the dedicated dosing coordinator on Day 1 (Visit 1). Subsequent eye drops on Day 1 are to be instilled by the subjects according to detailed written instructions. Subjects will be instructed to instill their drops into both eyes QID for the duration of the trial. Clinic staff will coach the subjects to dose themselves at approximately the same time every day e.g., morning, lunch time/mid-day, afternoon/early evening, and at bedtime. If a dose is missed, then the next dose should be administered on time. The dedicated dosing coordinator will inform subjects on how to store IMP (see Section 7.1.3) and dose IMP and how to complete their dosing diary.

Dosing should be continued until the day of the next Visit (should be at least 2 hours before first ophthalmic examination).

The bottles are designed for multiple use. Subjects will be instructed to only open one bottle at a time. They should be instructed not to discard the empty bottles but keep them in the kit box and return them at their next visit in the kit box. Subjects will record dosing in their dosing diary. Subjects will be instructed not to show the assigned IMP to the Investigator or site staff other than the dedicated dosing coordinator, unless instructed to do so.

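### Protocol 8.5: the Visit 4 example count for dosing noncompliance (more than 24) does not match the 20% rule it illustrates, which is first exceeded at 23 of 112

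*Protocol*

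**What the plan says.** Protocol Section 8.5 states the rule as a percentage: "If more than 20% of the responses to the total expected dose-taken prompts are checked" as not taken, or are blank or missing, "then the subject will be deemed noncompliant for dosing and a deviation recorded e.g., 12 checked". The sentence ends with the remaining conditions and the second count: "left blank, or missing at Visit 2 and Visit 3 and more than 24 at Visit 4". One sentence therefore holds a rule (over 20%) and two example counts, 12 at Visits 2 and 3 and more than 24 at Visit 4.

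The denominators follow from other sections:

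- Protocol 7.1.5 sets the frequency: "Subjects will be instructed to instill their drops into both eyes QID for the duration of the trial".
- Protocol 4.3 sets the visits: "Subjects will return to the clinic on Day 15±1 (Visit 2), 29±2 (Visit 3), and 57±2" for Visit 4.
- Protocol 4.3 also says "The dosing diary will be collected at the clinic during each visit and checked for compliance", so each count covers the interval since the previous visit.

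SAP Section 6.5.5 uses 56 as the expected number of doses to Visit 2. Neither document prints the expected number from Visit 3 to Visit 4 or explains where 24 comes from.

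**The concern.** An example attached to a numeric rule should give the same answer as the rule. At Visits 2 and 3 it does. At Visit 4, on the nominal schedule, it does not: two counts, 23 and 24, are over 20% but below the printed figure.

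This is a site instruction. Under Visits 2 and 3, Protocol 8.4.1 sends sites to Section 8.5 to calculate compliance. Its Visit 4 list asks only for collection and review of IMP and diary, and Section 8.5 is where a Visit 4 count is printed. A site working from the percentage and a site working from the count would reach different decisions on the same diary. What is at stake is whether a noncompliance deviation is recorded uniformly for the last interval, which covers half of the treatment period (28 of 56 days).

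**Working it through.** **Inputs.** Four doses a day (Protocol 7.1.5). Visits on Days 1, 15, 29 and 57, with windows of ±1 day at Visit 2 and ±2 days at Visits 3 and 4 (Protocol 4.3). Threshold: over 20% of expected prompts (Protocol 8.5).

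**Formula.** Expected prompts N = 4 × days in the interval. The first count that exceeds 20% is the whole-number part of 0.20 × N, plus 1.

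**Visits 2 and 3 (the plan's figure is reproduced).**
- N = 14 × 4 = 56, which agrees with the 56 in SAP 6.5.5.
- 0.20 × 56 = 11.2, so the first count over 20% is 12.
- 11/56 = 19.6% and 12/56 = 21.4%. The printed 12 is exact.

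**Visit 4 (the plan's figure is not reproduced).**
- N = (57 − 29) × 4 = 112.
- 0.20 × 112 = 22.4, so the first count over 20% is 23.

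| Missed of 112 | Per cent | Over 20%? | Meets printed count (25 or more)? |
|---|---|---|---|
| 22 | 19.6 | no | no |
| 23 | 20.5 | yes | no |
| 24 | 21.4 | yes | no |
| 25 | 22.3 | yes | yes |

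**Other ways of counting.**
- Partial first and last days, taken as 110 to 114 expected doses: the first count over 20% is still 23.
- Cumulative from Day 1 to Day 57: N = 56 × 4 = 224, 20% is 44.8, and the first count is 45.
- Reading the example as 24 or more: 23 is still missed.
- A cut-off of 25 is exact only for N = 120 to 124, a 30- or 31-day interval. The windows allow this, but it is not the nominal schedule.

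**Visit windows.** The interval from Visit 3 to Visit 4 can run from 55 − 31 = 24 days to 59 − 27 = 32 days, so N runs from 96 to 128 and 20% of N from 19.2 to 25.6. Applied as a fixed cut-off, the printed count would pass 24/96 = 25.0% and flag 25/128 = 19.5%. Those two extremes need Visits 3 and 4 at opposite ends of their windows.

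**Likely origin (an inference).** 24/112 equals 12/56, both 21.4%. The 24 looks like 12 doubled, which also doubles the rounding up from 11.2. Writing it as more than 24 then adds one more.

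**The case against.** The strongest defence is that the counts are examples. The percentage comes first in the sentence and the counts follow an e.g. As an illustration the Visit 4 figure is true, since 25 of 112 is over 20%. The rule is written on expected prompts, so it already scales with the subject's interval. This stands: under the rule itself, 23 or 24 missed doses of 112 are noncompliant, and nothing tells sites to prefer the count. What the defence does not remove is that the Visit 2 and 3 count sits exactly on the boundary, so a reader will take the Visit 4 count as a boundary too.

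Three stronger readings are tempting, and the documents do not support them.

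- A reader might infer that subjects missing 20.5% to 21.4% of doses will go unflagged. That happens only where a site applies the count in place of the percentage. The same condition applies to the visit-window errors.
- A reader might infer that per-protocol membership changes. Protocol 10.1 and SAP 6.5.3.2 exclude for significant deviations (major ones in SAP 6.5.2), and SAP 6.5.3 adds a blinded Sponsor review. No section classes a dosing deviation as significant or major.
- A reader might infer an effect on the main result or an error in the SAP. The primary estimands disregard non-optimal compliance (Protocol 10.4.5, SAP 6.5.7.3) and use the full analysis set. SAP 6.5.5 computes an overall compliance percentage, with a category break at 80%, and contains no count of 24.

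**Conclusion.** The mismatch is real and minor. On the nominal 28-day interval with four doses a day, the Visit 4 example is two counts too high: it starts at 25, whereas the 20% rule is first exceeded at 23. The consequence is possible inconsistency between sites in recording a dosing deviation for subjects with 23 or 24 missed doses. It reaches the per-protocol set, and so a sensitivity analysis, only if such deviations are judged significant. The primary full-analysis-set analysis is unaffected.

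The conclusion rests on counting each interval separately, which the collection and check of the diary at each visit supports, and on the nominal visit days, which the exact fit of 12 of 56 supports. The documents do not allow an estimate of how many subjects would have 23 or 24 missed doses.

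**What to change.** Reconcile the example with the rule in Protocol 8.5, in one of two ways:

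1. Keep nominal guides and correct the second: 12 or more of 56 at Visits 2 and 3, and 23 or more of 112 at Visit 4. Say that the percentage governs when the interval differs from nominal.
2. Drop the counts and define noncompliance as over 20% of the doses expected in the subject's actual interval between visits. This also removes the visit-window problem.

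The cost is one protocol sentence and, where sites had been using the printed count, a few more recorded deviations. The SAP has no count to correct.

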8.6 Subject Disposition

8.6.1 Completed Subjects

A completed subject is one who has not been discontinued from the trial.

8.6.2 Discontinued subjects

Notification of a subject discontinuation and the reason for discontinuation will be made to the CRO and/or trial sponsor and will be clearly documented in the eCRF as:

- Adverse event;
- Protocol violation;
- Lack of efficacy;
- Administrative reason (e.g. inability to continue, lost to follow up);
- Sponsor termination of trial;
- Subject choice (e.g. withdrawal of consent);
- Other

Subjects must be discontinued as outlined in [Section 5.6](#).

Subjects who discontinue for any reason after randomization will not be replaced.

8.7 Trial Termination

The whole trial may be discontinued prematurely in the event of any of the following:

- New information leading to unfavorable risk-benefit judgment of the IMP, e.g. due to:
 - Occurrence of significant previously unknown adverse reactions or unexpectedly high intensity or incidence of known adverse reactions, or
 - Other unfavorable safety findings.
- Sponsor's decision that continuation of the trial is unjustifiable for medical or ethical reasons.
- Poor enrollment of subjects making completion of the trial within an acceptable time frame unlikely.
- Discontinuation of development of the sponsor's IMP.
- Terminated or suspended upon request of Health Authorities.

Health Authorities and Institutional Review Boards (IRBs)/ Independent Ethics Committees (IECs) will be informed about the discontinuation of the trial in accordance with applicable regulations.

8.8 Trial Duration

An individual subject's participation will involve 5 visits over approximately a 10-week period, including screening. After the trial, subjects will be treated according to standard of care, at the discretion of the treating physician. The total duration of the trial from "first subject in" to "last subject out" is expected to be 8 months.

Subjects who completed trial NVU-003 without major protocol deviations, have been compliant with NVU-003 trial procedures and application of IMP may be invited to enroll

into trial NVU-004. NVU-004 will be a 12-month open-label safety extension trial of NVU-003 to assess the safety of topical NOV03 for the treatment of DED.

9 ADVERSE EVENTS

9.1 Adverse Event

An adverse event (AE) is defined as any untoward medical occurrence associated with the use of a drug in humans, whether or not the event is considered drug-related. An AE can therefore be any unfavorable and unintended sign (e.g., an abnormal laboratory finding), symptom, or disease occurring after the subject signature of the ICF without any judgment on causality.

If there is a worsening of a medical condition that was present prior to Visit 0, this should also be considered a new AE and reported. Any medical condition present prior to the administration of the IMP that remains unchanged or improved should not be recorded as an AE at subsequent visits.

Worsening of DED will be considered an AE only if the dry eye status of the subject exceeds their previous experiences with the condition. This will be determined by the subject and the investigator.

A clinically significant visual acuity worsening (defined as an increase of 0.22 or greater in logMAR score) from screening (Visit 0) will be considered an Adverse Event.

IMP includes the investigational drug under evaluation and any comparator drug, placebo, or any other medications required by the protocol given during any stage of the trial.

Documentation regarding the AE should be made as to the nature, date of onset, end date, severity, relationship to IMP, expectedness, action(s) taken, seriousness, and outcome of any sign or symptom observed by the physician or reported by the subject upon non-leading AE questioning.

AEs (both elicited and observed) and SAEs will be monitored throughout the trial. The investigator will promptly review all AEs for accuracy and completeness. All AEs will be documented on the appropriate source document and eCRF.

Adverse events recorded from the signing of informed consent through the last study visit must be reported, regardless of whether or not the AEs are considered study-related.

9.1.1 Severity

Severity of an AE is defined as a qualitative assessment of the degree of intensity of an AE as determined by the investigator or reported to him/her by the subject. The assessment of severity is made irrespective of relationship to IMP or seriousness of the event and should be evaluated according to the following scale:

- *Mild*: Event is noticeable to the subject but is easily tolerated and does not interfere with the subject's daily activities.
- *Moderate*: Event is bothersome, possibly requiring additional therapy, and may interfere with the subject's daily activities.
- *Severe*: Event is intolerable, necessitates additional therapy or alteration of therapy, and interferes with the subject's daily activities.

9.1.2 Relationship to Investigational Product

The relationship of each AE to the investigational drug should be determined by the investigator using these explanations:

- *Suspected*: A reasonable possibility exists that the investigational product caused the AE.
- *Not Suspected*: A reasonable possibility does not exist that the investigational product caused the AE.

Suspected adverse reaction means any AE for which there is a reasonable possibility that the investigational product caused the AE. "Reasonable possibility" means there is evidence to suggest a causal relationship between the investigational product and the AE. Types of evidence that would suggest a causal relationship between the investigational product and the AE include: a single occurrence of an event that is uncommon and known to be strongly associated with IMP exposure (e.g., angioedema, hepatic injury, Stevens-Johnson Syndrome); one or more occurrences of an event that is not commonly associated with IMP exposure, but is otherwise uncommon in the population exposed to the IMP (e.g., tendon rupture); an aggregate analysis of specific events observed in a clinical trial (such as known consequences of the underlying disease or condition under investigation or other events that commonly occur in the trial population independent of drug therapy) that indicates those events occur more frequently in the IMP-treatment group than in a concurrent or historical control group.

9.1.3 Expectedness

The expectedness of an AE should be determined based upon existing safety information about the IMP. The active ingredient of NOV03 is perfluorohexyloctane, which is a semifluorinated alkane with a well-established tolerability and safety profile. It has been tested in four PMCF studies and one phase 2 clinical trial up to now with >370 subjects that received NOV03 treatment. AEs of those studies have been listed in the Investigator's Brochure. Therefore, the following definitions will be used:

- *Unexpected*: An AE that is not listed in the investigator's brochure in the Adverse Reaction Section at the specificity or severity that has been observed.
- *Expected*: An AE that is listed in the investigator's brochure in the Adverse Reaction Section at the specificity and severity that has been observed.
- *Not Applicable*: Any AE that is unrelated to the IMP.

The investigator should initially classify the expectedness of an AE, but the final classification is subject to the sponsor's determination.

9.1.4 Outcome

The outcome of any AE will be determined and recorded using the following categories:

- Recovered/Resolved
- Recovering/Resolving
- Not Recovered/Not Resolved
- Recovered/Resolved with Sequelae
- Lost to Follow-up
- Fatal
- Unknown

9.2 Serious Adverse Events

An AE is considered serious if, in the view of either the investigator, medical monitor or sponsor, it results in any of the following outcomes:

- Death;
- A life-threatening AE;
 - Note: An AE is considered “life-threatening” if, in the view of either the investigator, medical monitor or sponsor, its occurrence places the subject at immediate risk of death. It does not include an AE that, had it occurred in a more severe form, might have caused death.
- Inpatient hospitalization or prolongation of existing hospitalization;
 - Note: The term “inpatient hospitalization” refers to any inpatient admission (even if less than 24 hours). For chronic or long-term inpatients, inpatient admission includes transfer within the hospital to an acute/intensive care inpatient unit. Inpatient hospitalization does not include: emergency room visits; outpatient/same-day/ambulatory procedures; observation/short stay units; rehabilitation facilities; hospice facilities; nursing homes; or clinical research/phase 1 units.
 - Note: The term “prolongation of existing hospitalization” refers to any extension of an inpatient hospitalization beyond the stay anticipated or required for the reason for the initial admission as determined by the investigator or treating physician;
- A persistent or significant incapacity or substantial disruption of the ability to conduct normal life functions;
 - Note: A serious adverse event (SAE) specifically related to visual threat would be interpreted as any potential impairment or damage to the subject’s eyes (e.g. hemorrhage, retinal detachment, central corneal ulcer or damage to the optic nerve).
- A congenital anomaly/birth defect;
- Medically important
 - Important Medical Events that may not result in death, be life-threatening, or require hospitalization may be considered serious when, based upon appropriate medical judgment, they may jeopardize the subject and may require medical or surgical intervention to prevent one of the outcomes listed in this definition. Examples of such medical events include allergic bronchospasm requiring intensive treatment in an emergency room or at home, blood dyscrasias or convulsions that do not result in inpatient hospitalization, or the development of drug dependency or drug abuse.

9.3 Procedures for Reporting Serious Adverse Events

All AEs and their outcomes must be reported to CRO, the trial sponsor, and the IRB/IEC as required by the IRB/IEC, federal, state, or local regulations and governing health authorities and recorded on the appropriate source document and eCRF page.

9.3.1 Reporting a Serious Adverse Event

To ensure subject safety, all SAEs, regardless of relationship to the IMP, must be immediately (i.e. within a maximum 24 HOURS after becoming aware of the event) reported to CRO Drug Safety [REDACTED] who will notify and forward documentation to the medical monitor and the trial sponsor for review. All information relevant to the SAE must be recorded on the appropriate SAE report form. Within 24 hours of knowledge of a new SAE, the investigator must enter the SAE information into the SAE eCRF, complete the SAE cover letter and send both the SAE cover letter and a pdf of the SAE eCRF, along with redacted relevant source documents to the CRO/Drug Safety [REDACTED] [REDACTED]

The information entered must contain sufficient information to enable medical assessment by the medical monitor. At a minimum, the initial SAE report should contain the following information:

- Subject's trial ID number
- Description of the Serious Adverse Event
- Date of the Serious Adverse Event
- Criterion for seriousness
- Preliminary assignment of causality to IMP

All information relevant to the SAE must be recorded on the appropriate case report forms. The investigator is obligated to pursue and obtain information requested by CRO Drug Safety [REDACTED] or, CRO and/or the sponsor in addition to that information reported on the case report form. All subjects experiencing a SAE must be followed up and the outcome must be reported. The investigator must obtain and maintain in his/her files all pertinent medical records, information, and medical judgments from colleagues who assisted in the treatment and follow-up of the subject; provide CRO Drug Safety [REDACTED] and the trial sponsor with a complete case history, which includes a statement as to whether the event was or was not suspected to be related to the use of the IMP; and inform the IRB of the AE within their guidelines for reporting SAEs.

All SAEs will be reported from the signature of Informed Consent until 30 days after the last administration of study drug.

All SAEs will be followed until resolution, stabilization, the event is otherwise, explained, or the subject is lost to follow-up.

Investigators are not obligated to actively seek SAE information from subjects that completed the study, but investigators are encouraged to notify the Sponsor, or designee, of any SAEs of which they become aware occurring at any time after a subject has discontinued or completed the study that they judge may be reasonably related to treatment with study drug.

